Secondary Outcomes	
 
• Change from baseline in KCCQ-TSS after 90 days of treatment.
 
• Change from baseline in log-transformed NT-proBNP level over 90 days of treatment.
 
• Change in NYHA class
 
• Days alive and out of hospital from study drug initiation until 90 days after initial hospital discharge.
 
• Days alive and out of hospital from study drug initiation until 90 days after randomization.
 
• Time to first occurrence of cardiovascular death or heart failure event until end of trial visit.
 
• Occurrence of HHF until 90 days after initial hospital discharge.
 
• Occurrence of chronic dialysis or renal transplant or sustained reduction of <math>\geq 40\%</math> eGFR, or 
 
- Sustained eGFR <math>< 15\text{mL/min}/1.73\text{m}^2</math> for patients with baseline eGFR <math>\geq 30\text{ mL/min}/1.73\text{m}^2</math>
 
- Sustained eGFR <math>< 10\text{mL/min}/1.73\text{m}^2</math> for patients with baseline eGFR <math>< 30\text{ mL/min}/1.73\text{m}^2</math>.
 
 
 
• Weight loss per mean daily loop diuretic dose after 15, 30, 60 and 90 days of treatment.
 
• Change from baseline in 6MWD at 90 days.
 
• Cost effectiveness of early initiation of empagliflozin for heart failure events avoided and quality-of-life years (QALY) gained.
 

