### Inclusion criteria:

1. Subject age >18 hospitalized for primary diagnosis of acute HF
2. Dyspnoea (exertional or at rest) and 2 of the following signs:
  - Congestion on chest X-ray

- Rales on chest auscultation
- Clinically relevant oedema (e.g.  $\geq 1+$  on a 0 to 3+ scale)
- Elevated jugular venous pressure

3. Stabilization criteria (while in the hospital):

- SBP  $\geq 100$  mmHg and no symptoms of hypotension in the preceding 24 hours
- No increase in i.v. diuretic dose for 24 h prior
- No i.v. vasodilators including nitrates within the last 24 h prior
- No i.v. inotropic drugs for 24 h prior

4. NT-proBNP  $\geq 1600$  pg/mL or BNP  $\geq 400$  pg/mL. (Patients with AF: NT-proBNP  $\geq 2400$  pg/mL or BNP  $\geq 600$  pg/mL. Measured during index hospitalization

5. Heart failure hospitalization that requires the treatment of a minimum single dose of 40 mg of i.v. furosemide( or Equivalent i.v loop diurectics defined as 20 mg of torsemind or 1mg of bumetanide)

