**Study procedure:**

Patients who meet inclusion and none of the exclusion criteria will be enrolled during hospitalization after stabilization. Patients should receive usual care per current relevant local and regional guidelines, as defined by their clinicians. Patients can be enrolled regardless of T2D status or ejection fraction. Enrolment is stratified according to patients with new-onset HF and worsening chronic HF. Informed consent will be signed before study enrolment. Baseline KCCQ-TSS and baseline 6MWT will be performed prior to study drug initiation and repeated at 30 and 90 days. Echocardiogram is not mandatory but permitted before subjects enrolment. Follow-up will be at 30 days, 60 days and 90 days.

Study drug will be dispensed by the research pharmacy provided by the study team (free of charge to the patient) as an open-label treatment.

Patients who meet inclusion and none of the exclusion criteria but declined study medication will be invited to be followed-up in a registry as reference group. These patients will follow the same baseline and follow-up assessment protocol (minus the study drug).

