**Study Endpoints:**

The primary outcome is clinical benefit at 90 days defined as a composite of all cause mortality, number of heart failure events (including hospitalization for HFs, urgent heart failure visits and unplanned outpatient visits), time to first heart failure event and change in KCCQ-TSS from baseline.

Secondary outcomes include improvement in KCCQ-TSS of  $\geq 10$  points after 90 days of treatment, change from baseline in log-transformed NT-proBNP levels over 90 days, days alive and out of hospital until 90 days, time to first occurrence of CV death or HFE until end of trial period, and change in 6-minute walk test and change in KCCQ-TSS between baseline and 90 days. Secondary safety endpoints include Occurrence of chronic dialysis or renal transplant or sustained reduction of  $\geq 40\%$  eGFR, or Sustained eGFR  $< 15\text{mL/min}/1.73\text{m}^2$  for patients with baseline eGFR  $\geq 30\text{mL/min}/1.73\text{m}^2$ , or Sustained eGFR  $< 10\text{mL/min}/1.73\text{m}^2$  for patients with baseline eGFR  $< 30\text{mL/min}/1.73\text{m}^2$ .

**Statistical analysis:** Categorical variables will be reported as percentages and counts, and continuous variables will be reported as means  $\pm$  standard deviations. Data analysis will be performed using STATA version 15 software (College Station, TX, USA).

Cost-effectiveness analysis will be performed to calculate incremental-cost effective ratio (ICER) for HFE avoided and QALY gained. Events of patients enrolled in the registry will be used as reference comparator. Costs will be based on Hospital Authority gazette prices for hospital admissions and visits.

*Table 1. Data to be collected in this study*

	Enrollment	30 days	60 days	90 days
Patient Informed Consent	x			
History including baseline characteristics	x			
Baseline co-morbidities:	x			

Baseline and in-hospital medications	x			
Physical examination include body weight	x	x	x	x
Laboratory test including NT-proBNP or BNP within 72hr of index admission, eGFR	x	x	x	x
Clinical events: all cause mortality, cardiovascular-associated death, A&E visit for acute heart failure, unplanned outpatient clinic visit, re-admission for heart failure	x	x	x	x
6MWD	x			x
Symptoms QOL assessment: NYHA class, KCCQ-TSS	x			x
Prescription records of SGLT2 inhibitors	x	x	x	x
Adverse drug effects	x	x	x	x

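### Table 1 accepts BNP where a secondary endpoint needs NT-proBNP, and ties the sample to admission rather than to the first dose

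*Protocol*

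**What the plan says.** The Protocol states the endpoint twice, both times on NT-proBNP alone. The Protocol Summary lists among the secondary outcomes "Change from baseline in log-transformed NT-proBNP level over 90 days of treatment". Section 2, Study Endpoints, has "change from baseline in log-transformed NT-proBNP levels over 90 days".

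Table 1 has a single laboratory row, "Laboratory test including NT-proBNP or BNP within 72hr of index admission, eGFR", marked at enrolment, 30, 60 and 90 days.

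Eligibility also accepts either peptide. The thresholds are 1600 pg/mL for NT-proBNP or 400 pg/mL for BNP, rising to 2400 or 600 in atrial fibrillation, and the sampling time is given only as "Measured during index hospitalization".

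Under Study procedure, patients "will be enrolled during hospitalization after stabilization". The same paragraph requires the baseline KCCQ-TSS and walk test to be done before the drug is started. It sets no such rule for the peptide.

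**The concern.** Two features of the Table 1 row do not fit the endpoint.

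- **Analyte.** The endpoint needs NT-proBNP at both ends. The row can be satisfied with BNP, or with different peptides at different visits. The Protocol's own paired thresholds show that the two are not on one scale. A patient with BNP at either end has no valid change, so who contributes to the endpoint may depend on which assay was ordered.
- **Timing.** The only window given is counted from admission, while the drug starts after stabilization. Entry requires a hospitalization treated with i.v. loop diuretic, so some decongestion before the first dose is part of the population's course. If the baseline sample is drawn early in the stay, the fall due to that decongestion enters a change that the Protocol Summary describes as occurring over 90 days of treatment. This would flatter the drug in a within-patient analysis.

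Both are rules about what is collected. An analysis plan cannot recover an assay that was not run or a sample that was not drawn at the right time.

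**Working it through.** The Protocol gives no figure for this endpoint, so there is none to reproduce. The check compares the passages and then shows the scale under stated assumptions.

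**1. Analyte.** The endpoint names NT-proBNP; the schedule names NT-proBNP or BNP. The threshold ratios are 1600/400 = 4.0 and 2400/600 = 4.0, and ln(4) = 1.39. If that ratio is taken as a rough conversion (assumption), a patient with BNP at baseline and NT-proBNP at follow-up would show a spurious rise of about 1.39 log units if the values were pooled by mistake.

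**2. Timing.** The window is 72 h from admission. Most stabilization conditions look back 24 h, for example "No increase in i.v. diuretic dose for 24 h prior", and none looks back further. The earlier trial cited in the Introduction reports a median of 3 days to stabilization and randomization, which equals 72 h. A sample inside the window can therefore fall before stabilization, after it or, in a patient enrolled early, after the first dose. The text fixes none of these.

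**3. The other columns.** A window counted from index admission cannot apply to the 30, 60 and 90 day columns of the same row. The row therefore mixes an index-stay rule with a follow-up schedule.

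**4. Precision lost to BNP-only patients.** Let p be the share without a usable NT-proBNP pair (assumption; not in the documents). With missingness unrelated to outcome and an unchanged standard deviation, the standard error grows by the factor 1/√(1 − p). This does not depend on the total enrolled.

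| p | factor | increase |
|---|---|---|
| 0% | 1.00 | 0% |
| 10% | 1/√0.90 = 1.05 | 5% |
| 20% | 1/√0.80 = 1.12 | 12% |
| 30% | 1/√0.70 = 1.20 | 20% |
| 50% | 1/√0.50 = 1.41 | 41% |

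**5. Shift from an early baseline.** Let f be the proportional fall between the sample and the first dose, and s the share of patients sampled before that fall (both assumptions). The mean log change is shifted by s × ln(1 − f).

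| f | s = 100% | s = 50% | s = 0% |
|---|---|---|---|
| 0% | 0 | 0 | 0 |
| 20% | −0.22 | −0.11 | 0 |
| 30% | −0.36 | −0.18 | 0 |
| 40% | −0.51 | −0.26 | 0 |

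The s = 100% column is the upper bound for each f.

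**The case against.** A reader might infer that Table 1 places the baseline before stabilization. The documents do not support that. The row is marked under enrolment, which follows stabilization, and the look-backs are short enough for a sample within 72 h of admission to come after it. Nor is sampling before the first dose a fault, since any baseline should be. What stands is that the sample is not tied to the first dose, although the KCCQ-TSS and walk-test baselines are.

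The whole phrase in the row, the BNP alternative included, may describe only the index sample used for eligibility. That reading is natural, because the 72 h clause cannot govern follow-up. But Table 1 then states neither the follow-up peptide nor the timing of the endpoint baseline, and the row still needs rewording.

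The study is single-centre, and the documents do not say which assay the hospital runs. The BNP-only share could be zero, so loss of patients is a possibility and not a fact. This stands, and the range above starts at 0%.

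Registry patients follow the same assessments, so a between-group comparison would share the baseline rule. A reader might still infer a biased comparison with the registry. The Protocol names the registry as comparator only for the cost-effectiveness analysis and states no between-group NT-proBNP comparison, so that inference goes too far. A shared schedule does not, however, restore missing NT-proBNP values or correct the within-patient change.

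The choice among several pre-dose values can be left to an analysis plan. That holds only if a suitable NT-proBNP value exists, which the schedule does not ensure.

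**Conclusion.** The point holds as a mismatch between a secondary endpoint and the schedule meant to supply it. Table 1 allows a compliant patient to have no NT-proBNP change, and it anchors the baseline to admission, so pre-drug decongestion may be counted as change on treatment. That this happens in every patient, or in any known share, does not follow from the text.

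The size cannot be derived from the documents. Under the assumed ranges, the standard error rises by 0-41% (BNP-only share 0-50%) and the log change shifts by 0 to 0.51 towards a larger fall (pre-dose fall 0-40%). The upper figure for the shift requires all patients to be sampled before decongestion. In a patient sampled after an early first dose, by contrast, the baseline would miss any drug effect up to that sample.

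The primary composite contains no natriuretic peptide in either of its two statements and is not affected. The row should be corrected, because the correction is cheap and the loss cannot be repaired afterwards.

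**What to change.** - Keep the either-peptide rule, measured at any time in the index stay, for eligibility only.
- In Table 1, separate the eligibility sample from the endpoint samples and remove the 72 h clause from the follow-up columns.
- Require NT-proBNP for treated and registry patients at the enrolment draw, after stabilization and before the first dose (for the registry, at the enrolment assessment), and at the 30, 60 and 90 day visits.
- Define that enrolment value as the baseline for the log NT-proBNP endpoint.

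The blood draws are already scheduled, so no visit is added. The cost is an NT-proBNP assay at enrolment where the eligibility value was BNP or was drawn earlier, and NT-proBNP in place of BNP at follow-up. The documents give no assay price; the charge should be small. If the hospital already runs only NT-proBNP, naming it costs nothing, and the only addition is a repeat assay where the eligibility sample was drawn before stabilization.

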Current guidelines recommend in-hospital echocardiogram in the clinical setting of new-onset or decompensated (6). However, echocardiogram is often delayed months after discharge or not performed at all under Hong Kong public hospital setting. As a result, initiation of guideline recommended therapies like ARB/ARNI/MRA/BB may be delayed for HFrEF patients awaiting echocardiogram or unnecessary for HFpEF patients. Out of the 4 guidelines recommended treatment for HF, only empagliflozin has proven benefits for the treatment of both HFrEF and HFpEF. Given that empagliflozin is well tolerated and its benefits are seen early, it may be reasonable to initiate empagliflozin early during index hospitalization even before the assessment of LVEF is available. However, costs remains a major barrier for early initiation of SGLT2-inhibitor.

The timing of SGLT inhibitors initiation in the treatment of acute HF is not established. In particular, new-onset acute HF is a group which is understudied in the major trials to date. This study aims to evaluate the efficacy and safety of in-hospital initiation of empagliflozin in patients hospitalized for new onset acute HF, regardless of LVEF for up to 90 days of follow-up.

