### **4. Potential Harm**

The EMPULSE study has shown overall safety of empagliflozin was consistent with previous findings, confirming the established safety profile of empagliflozin in patients with heart failure. Empagliflozin was well tolerated with fewer serious adverse events than was placebo (32.3% vs 43.6%). The incidences of worsening renal function and volume depletion were not common and were balanced between treatment groups. No ketoacidosis occurred in the empagliflozin groups.

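### Table 1's only adverse-event row is undefined and depends on attribution to a drug, so harms other than renal outcomes, deaths and heart failure events are not collected on an all-cause basis

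*Protocol*

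**What the plan says.** The Introduction states the aim: "This study aims to evaluate the efficacy and safety of in-hospital initiation of empagliflozin". Methods describes the study as open-label and non-randomized.

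Table 1 lists the data to be collected. Its single adverse-event row is "Adverse drug effects", marked at enrolment and at 30, 60 and 90 days. The protocol does not define the term or say which drug is meant. Table 1 has no row for adverse events or serious adverse events of any cause.

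Other rows also bear on safety, and none of them has a causality condition:

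- "Laboratory test including NT-proBNP or BNP within 72hr of index admission, eGFR", at all four time points.
- "Clinical events: all cause mortality, cardiovascular-associated death, A&E visit for acute heart failure, unplanned outpatient clinic visit, re-admission for heart failure", also at all four time points.

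The named safety endpoints, under Study Endpoints, are renal: "Secondary safety endpoints include Occurrence of chronic dialysis or renal transplant or sustained reduction of" at least 40% in eGFR, or sustained eGFR below a threshold that depends on baseline.

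Eligible patients who decline the drug may join a registry as a reference group. Study procedure says of them: "These patients will follow the same baseline and follow-up assessment protocol (minus the study drug".

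**The concern.** An adverse-event record limited to drug effects filters events by opinion before they reach the database. Here the opinion comes from staff who know who takes empagliflozin. The patients have acute heart failure and have received i.v. loop diuretics, so low blood pressure or volume depletion has a ready alternative explanation. An event explained that way does not belong in the row as worded.

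Two things are at stake. A low count in treated patients could be read as good tolerability when the recording rule produced part of it. Any comparison of these harms with the reference group would also rest on a row that does not mean the same thing in both groups. This is a data-collection rule, so a statistical analysis plan cannot repair it later: events that were never recorded cannot be analysed.

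**Working it through.** The protocol gives no figure on this point to reproduce. The check sets Table 1 against the aim, the safety endpoints and the registry procedure.

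**Step 1. Which harms are recorded whatever their cause?**

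| Harm | Where in Table 1 | Attribution needed? |
|---|---|---|
| eGFR decline | Laboratory row, all visits | No |
| Death, all-cause or cardiovascular | Clinical events row, all visits | No |
| Heart failure A&E visit or re-admission; unplanned clinic visit | Clinical events row, all visits | No |
| Volume depletion, hypotension, ketoacidosis (non-fatal) | Adverse drug effects row only | Yes |
| Non-fatal admission for a reason other than heart failure | Adverse drug effects row only | Yes |

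The gap is confined to the last two lines.

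**Step 2. Effect on the treated count.** Let p be the true proportion of treated patients with a harm of this kind, and f the fraction of those harms that staff attribute to the drug. The recorded proportion is p × f, and the share missed is 1 − f. The documents give neither p nor f. Taking f as an assumption:

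- f = 0.10: share missed 1 − 0.10 = 90%
- f = 0.25: share missed 1 − 0.25 = 75%
- f = 0.50: share missed 1 − 0.50 = 50%

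The serious-adverse-event rates quoted in Potential Harm are not used for p. They are overall rates and are not split to exclude deaths and heart failure admissions, which this study records anyway.

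**Step 3. Effect on a comparison with the registry.** The row can be read in two ways.

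- *Effects of the study drug.* A registry patient not taking an SGLT2 inhibitor cannot have an event. If no registry patient takes the class, the recorded difference is p × f − 0, which is never negative whatever the true difference. The row could then never show fewer such events on treatment. The overall comparison that the protocol cites ran in exactly that direction: 32.3% − 43.6% = −11.3 percentage points.
- *Effects of any drug.* Registry patients on usual care can have events, but the row counts effects of empagliflozin plus other drugs in one group and effects of other drugs alone in the other. Each event still passes through a judgement made with knowledge of treatment.

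Neither reading gives a like-for-like comparison of these harms.

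**The case against.** The strongest reply is that safety does not rest on this row. The named safety endpoints are renal, eGFR is measured at every visit, and deaths and heart failure events are recorded in both groups without any causal judgement. All of that stands. A reader might infer that adverse drug effects are the only safety item, or that the safety aim cannot be answered; the documents support neither. Nor is a fall in eGFR an example of a harm lost through attribution, because it is measured directly.

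A reader might also infer that registry patients must score zero. That follows only if the row means the study drug and no registry patient takes the class. The row does not say so. It is also marked at enrolment, registry patients take other drugs, and Table 1 separately tracks SGLT2 inhibitor prescriptions.

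Third, the protocol specifies no between-group safety analysis. The sentence "Events of patients enrolled in the registry will be used as reference comparator" stands in the cost-effectiveness paragraph, and the cited trial's adverse-event rates appear as background and rationale, not as a stated benchmark. This is fair and limits the point about comparison. It leaves the undercount in treated patients untouched, and Study procedure does call the registry a reference group in general terms.

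Finally, days alive and out of hospital is a secondary outcome and needs hospital days of any cause, so some non-heart-failure admissions may surface in practice. Table 1 names only heart failure re-admission, so this is not assured.

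**Conclusion.** The point holds in a limited form. Followed as written, Table 1 keeps non-fatal harms that are neither renal endpoints nor heart failure events only when someone judges them drug-caused, in a study where treatment is known and safety is a stated aim. The treated count for these harms could be too low, and it would not be comparable with the registry on either reading of the row. Renal safety, mortality and heart failure events are unaffected, so the aim is partly compromised, not defeated.

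The size cannot be derived from the documents. The 50% to 90% loss rests wholly on an assumed attribution of 50% down to 10%, and it applies only to the affected harms. It would be wrong to turn the cited trial's serious-adverse-event rates into expected counts here. The protocol gives no registry size, those rates are not split by type of event, and only about a third of that trial's patients had new-onset heart failure, whereas this protocol excludes patients with a documented history and a previous heart failure admission. This is a worthwhile, inexpensive correction.

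**What to change.** Replace the Table 1 row with *All adverse events and serious adverse events, regardless of causality*, recorded identically from enrolment to day 90 in treated and registry patients. Keep relatedness to the study drug as a separate field. State that the safety summary reports all-cause events, with drug-related events as a subset.

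The cost is more case-report-form entries at visits that already exist, and a higher reported event rate that will need to be read as all-cause. It needs no extra visits, tests or staff. The new row would also capture admissions for reasons other than heart failure, which days alive and out of hospital requires and Table 1 does not list.

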### **3. CONFIDENTIALITY OF DATA**

Paper and electronic dataset that contain patient's identity and confidential information will be stored in locked cabinets or password protected computers only accessible by the appointed research staff to prevent unauthorized access to data. The Investigator/Site will archive and retain all documents pertaining to the Study as per the applicable regulatory record retention requirements for a period of three (3) years after completion or early termination of the Study. The data can be destroyed after completion of storage period as agreed by principal investigator.

